Study Procedures – Because there may be significant heterogeneity in dialysis facilities and patient and staff populations across the 18 participating ESRD Networks, we will randomize dialysis facilities that were not included in formative testing within each ESRD Network region to either the multicomponent intervention (feedback report, webinar, and videos) or comparison group (usual care plus UNOS educational brochure). At baseline (Year 2, Q3-Q4), all eligible dialysis facility Medical Directors in both the intervention and control group will receive an email from their ESRD Network Executive Director a web-based survey (HIPAA-compliant surveymonkey) with informed consent. For those who consent to participate (in reporting secondary outcome measures), baseline surveys will then be administered. Within one week of this email (or immediately after for those that complete a baseline survey), all facility Medical Directors from participating facilities will be emailed a UNOS pamphlet and instructed to share with staff; intervention facilities will be emailed facility-specific performance feedback report and videos, and information about the educational webinar. At 3 months, all facility Medical Directors who consented to participate will be emailed follow-up surveys by their respective ESRD Network Executive Director to assess secondary outcomes. Our prior work has shown >90% response rates by Medical Directors when surveys are mailed directly from the ESRD Network.⁵³ Medical Directors will be offered an electronic gift card incentive (\$10) for participation.

Effectiveness Measure Outcomes – To test the effectiveness of this intervention, several outcomes will be assessed via surveys and surveillance data. Waitlisting data from 1 year post-intervention will be assessed using nationally available Dialysis Facility Report surveillance data in order to assess disparity reduction at the facility level. Follow-up surveys will be emailed to all Medical Directors at 3 months to test change in knowledge about the kidney allocation policy and whether Medical Directors have implemented

any staff training regarding the allocation policy within their dialysis facility, what methods the facility has used to educate ESRD patients about the kidney allocation policy, and whether the policy influenced facility Medical Directors' intent to refer more patients for transplantation.

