Measures are described below. Surveys will be pilot tested in formative phases and finalized with approval by the Dissemination Advisory Board.

1) Change in Waitlisting Disparity (Primary Outcome) – We will calculate facility racial disparity in waitlisting one year prior and post-intervention as the difference between the proportion of AA vs. whites waitlisted.

2) Change in Knowledge about the Kidney Allocation System (Secondary Outcome) – We will survey Medical Directors using a 20-question scale measuring knowledge about the kidney allocation system, and general transplant knowledge, based on a validated scale we have used among dialysis staff and patients.⁵⁴

3) Change in Staff Training about Kidney Transplant and the Allocation System (Secondary Outcome) – We will assess at baseline whether Medical Directors have trained their staff about transplantation and/or the details of the kidney allocation policy. We will ask whether the Medical Director provided training about transplant or the kidney allocation policy in the prior 3 months after intervention delivery, and information about training (e.g., did they hold a training session, send an email, watch video presentations, etc.). Details about trainings will be collected to inform best practices for staff training for future scale-up.

4) Evidence of Communication to Patients (Secondary Outcome) – To ensure that dialysis facility Medical Directors communicate information about the kidney allocation system to their staff and patients, we will track the educational video website usage by asking users to input user type, facility name, and location. This will allow us to track intervention dose and usage statistics such as number of uses by facility, time in application, etc. We have previously tracked other mobile educational initiatives through Google Analytics with success.⁵⁵

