Implementation	Extent to which an intervention is delivered as intended	1. Crude implementation index 2. Qualitative analysis of implementers vs. non-implementers
Maintenance	Long-term behavior change	Longer-term (1-year) adoption measures among a subset of facilities

implementers (n=5). At 1 year via phone interviews. These providers will be selected among the providers who completed the follow-up survey and already provided consent for the intervention. Phone interviews will be recorded and transcribed to help us better understand how to improve the intervention for the future. Providers who participate in the interview will be given \$30 gift cards as an incentive.

Other Measures. To explore potential moderators of the effectiveness of this system-level intervention, we will examine facility characteristics (region, facility size, profit status, etc), characteristics of patients in facilities (e.g., race, SES, comorbidities, etc), and neighborhood characteristics. We will include process measures for the intervention (receipt of intervention and self-report) to evaluate utility, value, satisfaction and reactions to intervention materials to ensure optimal future dissemination of interventions to other US dialysis facilities.

STATISTICAL ANALYSES

We will evaluate our main outcome of change in AA vs. white racial disparity reduction in waitlisting in the year post-intervention compared to the year prior to the intervention among the intervention vs. control facilities (intent to treat) using generalized linear models⁴⁸ to account for potential correlation of facilities within Networks. Secondary analyses will examine facility- and patient-level modifiers of the intervention. Change in each of the secondary outcomes will be examined. *We hypothesize that increasing provider knowledge about the allocation policy in facilities with racial disparities will reduce waitlisting disparities.* Follow-up interviews will be transcribed verbatim and a codebook will be developed for qualitative analysis. Thematic analysis of key facilitators and barriers will be conducted to inform practice change.⁵¹

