Sample Size and Power. With 18 ESRD Networks participating (representing 1500 dialysis facilities with a waitlisting disparity), we estimate a minimum of ~375 facilities (average of 70 patients/facility) in each control/intervention group (total N=750), after accounting for ~1% loss from facilities that may close in the 1-year evaluation and yearly fluctuation in waitlisting disparity. This will achieve 80% power (at $\alpha=0.05$) to detect a difference of 10% in the waitlisting disparity ratio (%AA waitlisted/%white waitlisted) in the intervention vs. control group at 1 year, assuming the same disparity ratio (0.6) by group at baseline and an intraclass correlation coefficient of 0.06 among patients in a facility (based on RaDIANT). We found a 36% disparity reduction in the RaDIANT study after 9 months³¹; thus we expect that a 10% effect within 1-year is achievable.

DATA AND SAFETY MONITORING PLAN (DSMP) - A Dissemination Advisory Board (comprised of members of the SEKTC, and regional and national partners in the kidney transplant community) will be responsible for finalizing interventional material including performance feedback reports, webinars, and educational videos; See DSMB section in eIRB 81580.

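### Facilities are randomised within ESRD Network, but the primary model does not say how Network enters it; fit the 18 Networks as fixed stratum terms

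*Combined protocol and SAP*

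**What the plan says.** Under Study Procedures, the protocol expects that "there may be significant heterogeneity in dialysis facilities and patient and staff populations across the 18 participating ESRD Networks". For that reason it assigns facilities "within each ESRD Network region to either the multicomponent intervention" or the comparison group. The facility is the randomised unit and Network is the stratum.

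The primary outcome (Effectiveness Measure Outcomes, item 1) is a facility-level quantity, the racial gap in waitlisting. It is calculated for the year before and the year after the intervention "as the difference between the proportion of AA vs. whites waitlisted".

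The Statistical Analyses section compares the change between arms by intention to treat, with generalized linear models meant "to account for potential correlation of facilities within Networks". That is all it says about Network. It names no Network term, random effect, correlation structure, robust variance or baseline covariate, and it does not refer back to the stratified randomisation.

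The only intraclass correlation in the plan is 0.06, under Sample Size and Power. It is for patients within a facility, not for facilities within a Network.

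**The concern.** When randomisation is stratified, the analysis should normally carry the strata. Otherwise the between-stratum variance that the design removed from the arm comparison stays in the estimated standard error.

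Here the stratum appears in the analysis section only as a nuisance correlation. An analyst could reasonably read that as a model with no Network term, a random intercept, Network fixed effects, or GEE/cluster-robust errors with Network as the cluster. These do not all have the same error rate. The p-value and confidence interval of the primary test would then depend on a choice that could be made after the data are seen.

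**Working it through.** **Inputs from the document.** 18 Networks; about 375 facilities per arm, 750 in total; alpha 0.05 and 80% power (Sample Size and Power); randomisation within Network (Study Procedures).

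**Assumptions.** Two-sided test, 1:1 allocation within each Network, and a share ρ of the outcome variance lying between Networks. The documents give no ρ, so a range of 0 to 0.20 is shown.

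**The plan's own power figure.** The stated 80% could not be reproduced.
- The design effect is 1 + (70 − 1) × 0.06 = 5.14. A two-sided ratio-of-ratios comparison then gives 25% power if the 10% means 0.60 to 0.66, and 57% if it means 0.60 to 0.70.
- Some variants come close, such as 82% for 0.60 against 0.70 with the facility as the unit. That one drops the stated intraclass correlation; others need choices the plan does not state.
- Sidedness, the meaning of 10% and the formula are not given, so the figure is not called wrong. Below, 80% is only a reference level.

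**Network left out, by formula.** Set the total variance to 1. With balance inside each Network, Network effects cancel from the arm difference, so its true variance is (1 − ρ) × 2/375. A model without Network estimates it as 2/375. Hence:
- type I error = 2[1 − Φ(1.96/√(1 − ρ))]
- power, when the stratified analysis has 80%, = Φ(2.802 − 1.96/√(1 − ρ))

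| ρ | 1.96/√(1 − ρ) | Type I error | Power |
|---|---|---|---|
| 0.02 | 1.980 | 4.8% | 79.4% |
| 0.05 | 2.011 | 4.4% | 78.5% |
| 0.10 | 2.066 | 3.9% | 76.9% |
| 0.15 | 2.126 | – | 75.0% |
| 0.20 | 2.191 | 2.8% | 72.9% |

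**Three versions, by simulation.** No true effect, 750 facilities, 18 Networks, balanced within Network, 8,000 trials per cell (Monte Carlo standard error about 0.24 points). Each cell gives type I error (%) for equal / unequal Network sizes.

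| ρ | No Network term | Network fixed effects | Cluster-robust on Network, uncorrected z |
|---|---|---|---|
| 0 | 4.4 / 4.9 | 4.5 / 5.0 | 7.1 / 8.1 |
| 0.05 | 4.7 / 4.2 | 5.1 / 4.7 | 7.8 / 7.2 |
| 0.10 | 4.2 / 4.0 | 5.1 / 5.0 | 7.6 / 8.0 |
| 0.20 | 3.3 / 3.1 | 5.5 / 5.1 | 7.4 / 8.1 |

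**Other readings.** A further simulation (unequal Networks, ρ from 0 to 0.15, 6,000 trials per setting) gave 4.8% to 5.6% for a random intercept. Cluster-robust errors with the 18/17 factor and a t reference on 17 degrees of freedom gave 5.0% to 5.9%. Another run of the corrected cluster-robust version gave 4.6% to 5.2%.

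**Effect varying between Networks.** With ρ = 0.05 and a between-Network standard deviation of the effect of 0.1 or 0.2 outcome standard deviations, Network fixed effects rejected a zero average effect in 6.1% or 9.1% of trials. Uncorrected cluster-robust errors gave 7.4% or 6.5%.

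**The case against.** The strongest reply is that the plan states the right purpose and merely leaves out detail. Several parts of that reply stand.

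- **The model class is adequate.** A reader might infer that a generalized linear model cannot handle Network. The documents do not support that: a generalized linear model with Network as a fixed effect does so, and it is the fix proposed here. The cited method reference is not available and may describe a correlated-data extension.
- **Not every natural reading fails.** A random intercept and corrected cluster-robust errors are close to nominal. The 7% to 8% figure belongs to the uncorrected version, which the protocol does not name. It remains one way to carry out the sentence as written.
- **Omitting Network does not create false positives.** A reader might infer inflation by analogy with cluster trials. Had whole Networks been randomised, with 750/18 = 41.7 facilities each, ρ = 0.05 would give a design effect of 1 + 40.7 × 0.05 = 3.03 and a type I error of 2[1 − Φ(1.96/√3.03)], about 26%. Study Procedures randomises facilities within Networks, so the error goes the other way.
- **The power loss is small.** Inflating the standard error by 1/√(1 − ρ) while holding the test at 5% would give 73.3% at ρ = 0.15. That overstates the loss, because only the estimated standard error grows; the correct figure is 75.0%. The outcome is also a change, from which stable Network differences cancel, so ρ may be low. At ρ = 0.02 the loss is 0.6 points.
- **Baseline adjustment is a separate addition.** No size is claimed for it here. It uses a quantity the plan already calculates.

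What remains is that the stratum used in the randomisation is not specified in the analysis, and the available choices give error rates from below 4% to about 8%.

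**Conclusion.** The point holds as a specification gap that should be closed; it is not a flaw that invalidates the trial. With Network omitted, the test is conservative, with about 1.5 to 3 points of power lost at assumed variance shares of 5% to 10%, and 0.6 to 5 points over 2% to 15%. With uncorrected cluster-robust errors on 18 Networks, the false-positive rate is about 7% to 8%. Network fixed effects stay at about 5% across the range.

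These sizes rest on an assumed Network share, 1:1 balance within Network, and a treatment effect common to all Networks. If the effect varies and the 18 Networks are viewed as a sample of possible Networks, fixed terms alone do not fully protect the test of the average effect. That is a reason to state the target as well. Since all 18 US Networks take part, the average effect over these Networks is a natural choice.

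**What to change.** Add to the Statistical Analyses section a sentence such as: *The facility-level outcome will be analysed in a linear model with terms for arm, ESRD Network (18 fixed stratum terms, matching the randomisation) and the facility's baseline waitlisting gap, with facility-level model-based or heteroscedasticity-robust standard errors. Cluster-robust standard errors on the 18 Networks will not be used without a small-sample correction.* State also that the target is the average effect over the 18 participating Networks.

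A linear model is itself a generalized linear model and suits an outcome defined as a difference in proportions. If the sponsor prefers a random intercept, or cluster-robust errors with a t reference on 17 degrees of freedom, either is acceptable if named in advance.

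Cost: 18 − 1 = 17 degrees of freedom out of about 750 facilities (17/750 = 2.3%), and no new data. It is a free improvement.
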